12.5 Reporting of Serious Adverse Events and Adverse Events

12.5.1 Reporting of Adverse Events to DAIT/NIAID

This section describes the responsibilities of the site investigator to report AEs to DAIT/NIAID reporting of AEs is required by 21 CFR and ICH E6 guidelines. Unless otherwise noted below in Section 12.5.2, Reporting of SAEs and Section 12.5.3, *Reporting of BILAG A Flares to DAIT/NIAID*, AEs must be recorded on the AE eCRF within five (5) days of discovery of the event.

12.5.2 Reporting of Serious Adverse Events to DAIT/NIAID

Site investigators will report all SAEs (see Section 12.2.4, *Serious Adverse Event*), regardless of relationship or expectedness within 24 hours of discovering the event. For SAEs, all requested information on the AE/SAE eCRF will be provided. However, unavailable details of the event will not delay submission of the known information. As additional details become available, the AE/SAE eCRF will be updated and submitted.

12.5.3 Reporting of BILAG A Flares to DAIT/NIAID

This section describes the responsibilities of the site investigator to report BILAG As to DAIT/NIAID via the AE/SAE eCRF. Timely reporting of AEs is required by 21 CFR and ICH E6 guidelines.

Site investigators will report all new BILAG As other than those noted at the screening visit, regardless of relationship or expectedness within 24 hours of discovering the event. For BILAG As, all requested information on the AE/SAE eCRF will be provided even if the BILAG A is not classified as an SAE. However, unavailable details of the event will not delay submission of the known information. As additional details become available, the AE/SAE eCRF will be updated and submitted.

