3.3.2 Safety Endpoints

The following specific events will be evaluated separately for each stage of the study:

- The incidence of Grade 3 or higher related AEs.
- The incidence of Grade 3 or higher infections.
- The incidence of renal dysfunction, defined as Grade 3 or higher chronic kidney disease with eGFR < 30 ml/min per 1.73 m².
- The incidence of Grade 3 or higher hypertension, defined as a systolic blood pressure ≥ 160 mm Hg or a diastolic blood pressure of ≥ 100 mm Hg.

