5.4 Risks of Withdrawal of Lupus Medications

During Stage 1, consenting participants will withdraw from current lupus medications. Withdrawal of lupus medications per protocol prior to randomization into Stage 2 could lead to disease exacerbation or flare. After signing of consent, the participant will receive a corticosteroid injection, which may be repeated an additional 2 times to achieve amelioration of symptoms. The use of corticosteroid injections which naturally wane in their effects gradually is a mitigation strategy for these risks.

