12.2 Definitions

12.2.1 Adverse Event (AE)

Any untoward or unfavorable medical occurrence associated with the participant's participation in the research, whether or not considered related to the participant's participation in the research (modified from the definition of adverse events in the 1996 ICHE-6 Guidelines for Good Clinical Practice) (from OHRP "Guidance on Reviewing and Reporting Unanticipated Problems Involving Risks to Subjects or Others and Adverse Events (1/15/07)" <http://www.hhs.gov/ohrp/policy/addevntguid.html#Q2>)

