12.3.2 Attribution Definitions

The relationship, or attribution, of an AE to the study therapy regimen or study procedure(s) will initially be determined by the site investigator and recorded on the appropriate AE eCRF. Final determination of attribution for safety reporting will be determined by DAIT/NIAID. The relationship of an AE to study therapy regimen or procedures will be determined using the descriptors and definitions provided in Table 12.1.

For additional information and a printable version of the NCI-CTCAE manual, consult the NCI-CTCAE web site:
<http://ctep.cancer.gov/reporting/ctc.html>.

Table 12.1 Attribution of Adverse Events

Code	Descriptor	Relationship (to primary investigational product and/or other concurrent mandated study therapy or study procedure).
UNRELATED CATEGORY		
1	Unrelated	The adverse event is clearly not related; there is insufficient evidence to suggest a causal relationship.
RELATED CATEGORIES		
2	Possible	The adverse event has a reasonable possibility to be related; there is evidence to suggest a causal relationship.
3	Definite	The adverse event is clearly related.

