13.4.4 Analyses of Secondary Safety Endpoints

Safety analyses will be performed on the safety sample and will be assessed by summarizing AEs separately for each stage of the study. The length of time participants are followed within each stage is variable and could depend on if a participant meets treatment failure. To account for potential differential duration of study participation, AE summaries by treatment group will include the number of events per person-year in addition to the number and percentage of events and participants experiencing events. AEs and SAEs will be summarized by system organ class, preferred term, and severity grade.

Safety endpoints identified in Section 3.3.2 Safety Endpoints, will be summarized and listed separately for each stage of the study. For each such endpoint, the number of events per person-year as well as numbers and percentages of events and participants who experience these events will be summarized overall in Stage 1 and by treatment group in Stage 2 and 3. No formal statistical testing will be performed to compare safety between treatment groups.

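### Aggregate adverse-event rates by arm include lupus flares, so they mix loss of efficacy with harm and can dilute an MMF excess

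*Combined protocol and SAP*

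**What the plan says.** - **Reporting of flares (12.5.3).** "Site investigators will report all new BILAG As other than those noted at the screening visit", whatever their relationship to treatment and within a day of discovery. Seriousness does not matter: "For BILAG As, all requested information on the AE/SAE eCRF will be provided even if the BILAG A is not classified as an SAE". Section 12.5.1 names 12.5.3 as an exception to the five-day AE recording rule, so the plan treats these reports as AEs.
- **Other flares (12.2.1, 12.3.1).** The AE definition has no exclusion for lupus activity, and events are recorded from Grade 2 upward.
- **Attribution (Table 12.1).** One code covers "Relationship (to primary investigational product and/or other concurrent mandated study therapy or study procedure". Section 5.4 notes that "Withdrawal of lupus medications per protocol prior to randomization into Stage 2 could lead to disease exacerbation or flare".
- **Safety endpoint (3.3.2).** The first listed is "The incidence of Grade 3 or higher related AEs".
- **Analysis (13.4.4).** "AEs and SAEs will be summarized by system organ class, preferred term, and severity grade". By-arm summaries give counts, percentages and events per person-year, with no formal test. Lupus activity is not separated. Sections 13.4.3 and 13.4.6 leave some details to the SAP, but 13.4.4 leaves none.
- **Primary endpoint (3.5.1).** A BILAG flare rated by the investigator as moderately or much worse is one route to treatment failure. The others are steroid injection or new or increased lupus medication, and permanent discontinuation for any reason.

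**The concern.** One event can count both as lost efficacy and as an adverse event. The design expects most placebo participants to lose their steroid response, and the trial is sized on a lower failure rate with MMF. If MMF works, flares recorded as AEs will be more frequent on placebo. They then raise the placebo AE, SAE and possibly related-AE totals for a reason unrelated to drug toxicity, and any MMF excess in those totals looks smaller than it is. With no formal safety test, these descriptive totals are a main part of the safety comparison, so what they contain matters. The events-per-person-year measure, added to handle unequal follow-up, can widen the flare imbalance, because failure also shortens Stage 2 exposure.

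**Working it through.** **Planning rates (13.7).** There are 60 participants per arm, with Week 24 failure-free proportions of 15% (placebo) and 35% (MMF). Exact enumeration of the unpooled Z-test at two-sided 0.05 gives 73.8% power, against the stated 74%. With MMF at 37% it gives 80.7%, against the stated 80% or more. The hazard ratio is ln(0.35)/ln(0.15) = 0.553, against the stated 0.55.

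**Failures by Week 24.** Placebo 0.85 × 60 = 51; MMF 0.65 × 60 = 39.

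**Person-time.** I use the plan's hazard that doubles at Week 12 and assume that Stage 2 exposure ends at failure. With h = −ln S(24)/36 per week, the area under S(t) to Week 24 is (1 − e^(−12h))/h + e^(−12h)(1 − e^(−24h))/(2h). This gives 0.2398 years per participant on placebo and 0.3106 on MMF, or 14.4 and 18.6 person-years per arm.

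**Flare AEs.** Let f be the share of failures that reach the AE form as one flare event in the category being counted. The documents do not give f.
- Counts: 51f against 39f, a gap of 20f percentage points (MMF:placebo ratio 39/51 = 0.76).
- Rates per person-year: 0.85f/0.2398 = 3.545f against 0.65f/0.3106 = 2.093f, a gap of 1.452f (ratio 0.59).
- At f = 20%: 10.2 against 7.8 events, 4 percentage points, and 0.71 against 0.42 per person-year, a gap of 0.29.

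**Effect on an assumed MMF excess.** Every non-flare rate below is an assumption. On the person-year scale the observed ratio is (non-flare MMF + 2.093f)/(non-flare placebo + 3.545f), and the excess is cancelled at f = (difference in non-flare rates)/1.452. On the percentage scale, with flare and non-flare events taken as independent, an arm's rate is 1 − (1 − a)(1 − f × failure proportion), where a is its non-flare rate.

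| Assumed non-flare, placebo vs MMF | True contrast | f = 10% | f = 20% | Cancelled at f |
|---|---|---|---|---|
| 0.1 vs 0.2 per person-year | ratio 2.0 | 0.90 | 0.76 | 7% |
| 0.2 vs 0.4 per person-year | ratio 2.0 | 1.10 | 0.90 | 14% |
| 0.3 vs 0.6 per person-year | ratio 2.0 | 1.24 | 1.01 | 21% |
| 5% vs 10% | +5 points | +2.78 | +0.55 | 22% |
| 5% vs 15% | +10 points | +7.45 | +4.90 | 39% |
| 40% vs 55% | +15 points | +12.83 | +10.65 | 69% |

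For the last row, the difference is 0.15 − f(0.60 × 0.85 − 0.45 × 0.65) = 0.15 − 0.2175f, which is zero at f = 0.15/0.2175 = 69%.

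Dilution occurs in every row. The break-even runs from 7% to 69%, according to the assumed rates and the scale. With flares tabulated apart, the flare term drops out and the true contrast is recovered.

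**The case against.** The strongest reply is that little of this is fixed by the documents.

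- **Size of f.** Form entry is explicit only for new BILAG A events. Section 4.1 describes flares in this population as mostly moderate, and 3.5.1 ties moderate flare to BILAG B. Failure also includes discontinuation for any reason, so f cannot be expected to approach 100%. For the related-AE endpoint, f is narrower still: the flare must be Grade 3 or higher and coded as related, and no passage maps BILAG A to a CTCAE grade. All of this stands. A reader might infer that an MMF excess will be reversed. The documents do not support that, because they give neither f nor any expected AE rate.
- **Attribution.** A reader might also infer that a flare caused by drug withdrawal counts as related under a stated rule. Table 12.1 does not name withdrawal. Withdrawal must be complete by the Stage 2 Randomization Visit (3.1.1), so calling it concurrent with Stage 2 is debatable, and final attribution for safety reporting rests with DAIT/NIAID. It is a plausible reading only, supported by 5.4 and by 13.4.1.3, which lets starting withdrawal qualify a participant for the safety population.
- **Existing protection.** Tables by system organ class and preferred term show diarrhea, cytopenias and infections by arm. Infection and hypertension are separate endpoints, largely untouched by flare; renal dysfunction could be touched only by renal flare. Flares have their own exploratory indices (3.4.1), and the DSMB has separate BILAG A and infection triggers (12.8.2.2). This confines the problem to the aggregate totals and the related-AE endpoint. It does not repair those, and a flare coded as arthritis or rash stays mixed even at preferred-term level.
- **Intent.** Severe flare after mandated withdrawal is a genuine participant risk, so counting it as a safety event is defensible. That supports keeping a version with flares, not having only that version.

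**Conclusion.** The point holds for the overall AE and SAE summaries and for the Grade 3+ related-AE endpoint. Followed as written, the plan puts efficacy events into these by-arm rates, and at its own planning rates the imbalance favours MMF by 20f percentage points or 1.452f events per person-year. The person-year figure rests on the plan's hazard shape and on exposure ending at failure. Participants who fail, start other lupus medication and stay under observation to Week 24 would pull the ratio from 0.59 towards 0.76.

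Dilution of an MMF excess follows for any f above zero if MMF lowers failure as planned. Its size, and whether it could amount to reversal, cannot be settled from the documents. Nor do they support the wider inference that the safety tables as a whole fail to describe drug harm: preferred-term tables and the infection and hypertension endpoints remain largely informative. It should be changed because the remedy is cheap and attribution by cause is hard to reconstruct reliably afterwards.

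**What to change.** 1. In 13.4.4, flag AEs that are SLE disease activity, including every BILAG A report.
2. Present overall AE, SAE and Grade 3+ related-AE summaries by arm both with and without flagged events, as counts, percentages and events per person-year. Use the version without them to describe drug toxicity, and keep the version with them to describe participant risk.
3. On the AE eCRF, record whether a related event is attributed to study drug, corticosteroid injection or medication withdrawal, since Table 12.1 has one code for all.

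The cost is one flag, one attribution field and a second set of tables. BILAG A reporting and the DSMB triggers stay as they are. A with/without table could partly be derived from preferred terms and BILAG data at analysis, but the cause of a related event needs to be captured when it is reported.

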12.5.4 Reporting to FDA

This clinical study has been granted exemption from IND regulations by the FDA in accordance with 21 CFR 312.2(b) of the regulations, therefore, AEs will not be reported to the FDA by the study sponsor (NIAID).

12.5.5 Reporting of Adverse Events to the IRB

All investigators shall report AEs, including expedited reports, in a timely fashion to the single IRB of record in accordance with applicable regulations and guidelines.

SAEs that are determined by DAIT/NIAID to have potential impact on the safety of all trial participants will be distributed by the DAIT/NIAID (or designee) to all participating site investigators and the single IRB of record.

12.6 Pregnancy Reporting

The investigator shall be informed immediately of any pregnancy in a study participant. A pregnant participant shall be instructed to stop taking investigational study medication. The investigator shall counsel the participant and discuss the risks of continuing with the pregnancy and the possible and unknown effects on the fetus. Monitoring of the pregnant participant shall continue until the conclusion of the pregnancy.

The investigator shall report all pregnancies to DAIT/NIAID via the SCCC within 1 business day of becoming aware of the event using the Pregnancy eCRF. All pregnancies identified during the study shall be followed to conclusion and the outcome of each must be reported. The Pregnancy eCRF shall be updated and submitted to the SCCC when details about the outcome are available.

Information requested about the delivery shall include:

- Gestational age at delivery
- Birth weight, length, and head circumference
- Gender
- Appearance, pulse, grimace, activity, and respiration (APGAR) score at 1 minute, 5 minutes, and 24 hours after birth, if available
- Any abnormalities

All pregnancy complications that result in a congenital abnormality, birth defect, miscarriage, and medically indicated abortion - an SAE shall be submitted to the SCCC using the SAE reporting procedures described above (Section 12.5.1, *Reporting of Serious Adverse Events to DAIT/NIAID*).

If a pregnancy occurs in a partner of a participant, the male participant whose partner gets pregnant will inform the investigator of the pregnancy. The participant will be encouraged to use barrier methods for the remainder of the pregnancy. The pregnant partner should see their Obstetrician. Data on partner pregnancies will not need to be collected for this study.

12.6.1 Mycophenolate REMS Program

ALE10 investigators are required to enroll in the FDA's Mycophenolate REMS program. An investigator will be required to report any pregnancy occurring in an ALE10 female participant while she is taking MMF or within the first 6 weeks following discontinuation of MMF treatment to the Mycophenolate Pregnancy Registry, which is part of the MMF REMS program. Participants will be required to participate in MMF REMS program as well.

12.7 Reporting of Other Safety Information

An investigator shall promptly notify DAIT/NIAID via the SCCC within 24 hours when an "unanticipated problem involving risks to participants or others" is identified, which is not otherwise reportable as an AE.

12.8 Review of Safety Information

12.8.1 Medical Monitor Review

The DAIT/NIAID Medical Monitor shall receive monthly reports from the SCCC compiling new and accumulating information on AEs, SAEs, and pregnancies recorded by the study sites on appropriate eCRFs.

In addition, the Medical Monitor shall review and make decisions on the disposition of the SAE and pregnancy reports received by the SCCC (See Sections 12.5.1, *Reporting of SAEs to DAIT/NIAID*, and 12.6, *Pregnancy Reporting*).

12.8.2 DSMB Review

12.8.2.1 Planned DSMB Reviews

The DSMB shall review safety data at least yearly during planned DSMB Data Review Meetings. Data for the planned safety reviews will include, at a minimum, a listing of all reported AEs and SAEs.

SAEs that are determined by DAIT/NIAID to have potential impact on the safety of all trial participants will be distributed by DAIT/NIAID to the DSMB and all participating site investigators.

12.8.2.2 Ad hoc DSMB Reviews

In addition to the pre-scheduled data reviews and planned safety monitoring, the DSMB may be called upon for *ad hoc* reviews. The DSMB will review any event that potentially impacts safety at the request of the Protocol Chair or DAIT/NIAID. In addition, the following events will trigger an ad hoc comprehensive DSMB Safety Review:

- Any death that occurs during the study.
- BILAG A flares in Cardiorespiratory, Neuropsychiatric, Gastrointestinal, Ophthalmic, Renal, or Hematological Systems occurring in
 - 3 or more of the first 10 randomized participants or
 - 30% or more of randomized participants at any time point after the 11th participant is randomized.
- Infections requiring hospitalization or > 1 dose of intravenous antibiotics in
 - 3 or more of the first 10 randomized participants or
 - 30% or more of randomized participants at any time point after the 11th participant is randomized.

After review of the data, the DSMB will make recommendations regarding study conduct and/or continuation.

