4.3 Exclusion Criteria

Participants who meet any of the following criteria are not eligible for randomization as study participants:

1. Inability or unwillingness of a participant to understand and provide written informed consent or comply with the study protocol.
2. BILAG A (severe) disease in the Cardiorespiratory, Neuropsychiatric, Gastrointestinal, Ophthalmic, Renal, or Hematological Systems.
3. Severe or unstable nephritis defined as any of the following:
 - a. History of confirmed Class 3-5 nephritis within the last 2 years,

- b. History of confirmed Class 3-5 nephritis > 2 years ago in the absence of documented treatment including both induction and maintenance therapy,
- c. UPCR > 1 g/g at screening,
 - If UPCR is > 0.5 g/g and ≤ 1 g/g at screening, then a second assessment must be completed with at least 1 week between assessments. If the second assessment is > 1 g/g or has increased by ≥ 0.3 g/g, then the participant is excluded.

4. Evidence of chronic kidney disease defined as eGFR < 45 mL/min per 1.73 m² at screening, where $175 \times (\text{Creatinine}/88.4) - 1.154 \times (\text{Age}) - 0.203 \times (0.742 \text{ if female}) \times (1.212 \text{ if of African descent})$ [5].

5. History of cirrhosis or chronic liver disease unrelated to SLE other than fatty liver disease.

6. History, within 1 year of the Screening Visit, of uncontrolled SLE that would have warranted a BILAG A (except mucocutaneous, constitutional, musculoskeletal) including, but not limited to, hemolytic anemia, neuropsychiatric lupus, or interstitial lung disease.

7. Uncontrolled HTN at the Screening or Randomization Visits defined as a blood pressure > 150/100 with or without treatment, not to exceed 3 complementary antihypertensive treatments.

8. Any of the following laboratory values during screening:

- a. Hemoglobin (Hg) < 8.0 g/dL,
- b. WBC < 2.0 × 10⁹ cells/L,
- c. ANC < 1.0 × 10⁹ cells/L,
- d. Platelets < 60 × 10⁹ cells/L at screening,
 - If platelets < 70 × 10⁹ cells/L at screening, platelet count should be retested 2 weeks later. If platelets are < 60 × 10⁹ cells/L at retest, participant will be excluded
- e. AST or ALT > 2.5 times the ULN,
- f. Serum IgG levels < 5 g/L

9. Use of ≥ 40 mg/day of prednisone within 4 weeks prior to the Screening Visit or use of > 20 mg/day of prednisone at screening.

10. Unwilling or unable to taper to ≤ 10 mg/day of prednisone or equivalent by the day of randomization.

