13.4.1.3 Safety Population

The safety population will include all participants who receive at least one IM injection of a long-acting corticosteroid or who initiate withdrawal of lupus medications in Stage 1. The safety population will be used for all safety analyses. Analysis performed on the safety population will be according to the treatment actually received in both Stage 2 and Stage 3.

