Although the number per cluster will be random, if the 7 clusters are evenly distributed in the lupus population, then the number achieved for any given cluster will likely include 11 to 24 individuals (i.e. $> 90\%$ chance) or approximately 5 to 12 per arm. Hence, we are likely to have adequately powered comparisons for at least some clusters.

For Stage 3, we anticipate that at least 48 (80%) among those randomized to placebo in Stage 2 and approximately 36 (60%) among those randomized to MMF in Stage 2 will be eligible for re-randomization to MMF or MMF plus voclosporin. For Stage 3 analyses, we will have 4 groups defined by the cross-classification of Stage 2 and Stage 3 treatment assignments, as follows:

Stage 2 Randomization

Stage 3 Re-randomization	MMF	Placebo MMF
MMF + voclosporin	n_{MMF_Combo} (~18)	$n_{placebo_Combo}$ (~24)
MMF + placebo voclosporin	n_{MMF_MMF} (~18)	$n_{placebo_MMF}$ (~24)

Stage 3 is intended to explore baseline (pre-re-randomization) gene expression patterns and their associations with response (or non-response) to MMF and MMF plus voclosporin, and to describe differences in those associations between the 2 arms. Gene expression patterns may include immunologically-homogeneous clusters defined at screening, gene expression at the Stage 2 Day 0 Randomization Visit, or differential expression observed during the Stage 2 treatment period. Among those randomized to placebo in Stage 2, if we re-randomize 24 to MMF, we anticipate 8-12 responders (i.e. 35-50% who have not failed by Stage 2 Week 24) and 12-16 non-responders on which to evaluate baseline gene expression patterns. In the MMF plus voclosporin arm, the number of responders is expected to be at least as high as MMF alone. Stage 3 is exploratory and not powered to test a pre-specified hypothesis.

14 Identification and Access to Source Data

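### The flare and infection triggers for ad hoc DSMB review use only Stage 2 randomized participants, so they omit people harmed in Stage 1 and never randomized, and dilute a Stage 3 combination-arm excess about 2.9-fold

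*Combined protocol and SAP*

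**What the plan says.** Protocol section 12.8.2.2, repeated in the synopsis under Study Stopping Guidance, lists three events that automatically lead to an ad hoc DSMB review. The first is "Any death that occurs during the study". The other two are rates: BILAG A flares in six organ systems, and infections needing hospitalization or more than one dose of IV antibiotics. Each rate trigger has an early limb, "3 or more of the first 10 randomized participants or", and a later limb, "30% or more of randomized participants at any time point after the 11th participant is randomized". No separate denominator is given for Stage 1, for Stage 3 or for any arm.

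The same section allows review on request: "The DSMB will review any event that potentially impacts safety at the request of the Protocol Chair or DAIT/NIAID". Planned DSMB reviews take place at least yearly (12.8.2.1). The synopsis states that no pre-specified criteria stop the study, so these are review triggers and not stopping rules.

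Other sections treat the stages as separate risks. Section 5.4 says: "Withdrawal of lupus medications per protocol prior to randomization into Stage 2 could lead to disease exacerbation or flare". Section 13.4.1.3 defines the population for safety analyses more widely than the triggers do: "The safety population will include all participants who receive at least one IM injection of a long-acting corticosteroid or who initiate withdrawal" of lupus drugs in Stage 1. Sections 3.3.2 and 13.4.4 evaluate safety separately by stage, and by treatment group in Stages 2 and 3.

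**The concern.** Two groups fall wholly or largely outside the rate triggers.

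**Stage 1.** Exclusion 2 in section 4.3 bars "BILAG A (severe) disease in the Cardiorespiratory, Neuropsychiatric, Gastrointestinal, Ophthalmic, Renal, or Hematological Systems", the same six systems as the flare trigger. Exclusion 20 bars a Grade 2 or higher infection that has not resolved by randomization. Someone who develops either after drug withdrawal is not randomized and so is not counted, however many such cases there are.

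**Stage 3.** Only part of the 120 will receive MMF plus voclosporin, but all 120 stand in the denominator. Section 5.6 says that voclosporin has not been evaluated in SLE without nephritis. Stage 3 treatment lasts at most 24 weeks, so a participant can complete it between yearly reviews. A trigger meant to bring a review forward should be able to respond to an excess in that arm.

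**Working it through.** **Inputs from the plan (13.7, 3.1.3).** 120 randomized 1:1, so 60 per arm. Of the placebo arm, at least 48 (80%) are expected to enter Stage 3; of the MMF arm, "approximately 36 (60%) among those randomized to MMF in Stage 2 will be eligible for re-randomization". Stage 3 allocation is 1:1.

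**Reproducing the plan's counts.** 0.80 × 60 = 48 and 0.60 × 60 = 36. Halved, these give 24 and 18, which match the plan's table. The combination arm is 24 + 18 = 42, or 42/120 = 35% of those randomized.

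**Threshold.** 0.30 × 120 = 36 participants. With no events elsewhere, 36/42 = 86% of the combination arm must be affected. The dilution factor is 120/42 = 2.9. If the other 78 have event rate b, the combination-arm rate at which the expected total reaches 36 is (36 − 78b)/42:

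- b = 5%: 32.1/42 = 76%
- b = 10%: 28.2/42 = 67%
- b = 13%: 25.9/42 = 62%

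**Event rates are assumptions.** The only figures in the documents are serious infections of 12% with voclosporin/MMF and 13% with placebo/MMF, in nephritis trials (1.5.2.3). No rate of organ-threatening BILAG A flares is given for this population.

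**Probability of firing at n = 120.** This is P(X + Y ≥ 36), with X ~ Bin(42, combination rate) and Y ~ Bin(78, b), computed exactly:

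| Rate in the other 78 | Combination 30% | 40% | 50% | 60% |
|---|---|---|---|---|
| 5% | <0.001% | 0.007% | 0.3% | 4.3% |
| 10% | 0.02% | 0.5% | 5.7% | 27% |
| 13% | 0.2% | 2.7% | 16% | 48% |

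**The same 30% threshold within the arm, also at full accrual.** 0.30 × 42 = 12.6, so 13 participants. P(Bin(42, p) ≥ 13) is 0.2% at p = 13%, 6% at 20%, 50% at 30%, 91% at 40% and 99.6% at 50%.

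**Early denominators.** The current rule applies throughout accrual, so a single look understates it. A simulation applied both limbs, with the 30% limb checked from the 12th participant on and 35% of participants on the combination:

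| Others / combination | Ever fires | Fires at 60 randomized or later |
|---|---|---|
| 5% / 40% | 31% | about 1.5% |
| 5% / 50% | 47% | about 8.6% |
| 10% / 40% | 46% | about 7.7% |

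The probabilities are higher again at 10% / 50%. All are overestimates for Stage 3, because the simulation treats each outcome as known at randomization, whereas Stage 3 events come later, when the denominator has already grown.

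**Stage 1.** No probability can be computed, because the documents do not say how many people are expected to be withdrawn from drugs and not randomized. For them the contribution to both rate triggers is zero by definition.

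**The case against.** The strongest objection is that the triggers are not the only protection. Any death in any stage prompts review, and the Protocol Chair or DAIT/NIAID can ask for review of any event. Sites report SAEs and new BILAG As since screening within 24 hours (12.5.2, 12.5.3), AEs are collected from consent (12.4.1), the Medical Monitor receives monthly reports (12.8.1), and participants who are withdrawn and then screen-fail have a safety visit (8.1.1). All of this stands. A reader might infer that no automatic safeguard covers Stages 1 and 3; the any-death trigger refutes that. But death is a late signal, and the other routes set no rate that obliges a review.

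A reader might also infer that no Stage 1 event can count. That goes too far. Exclusion 20 does not bar an infection that has resolved, and the plan does not say whether a Stage 1 event counts once the person is randomized. The omission is certain only for people never randomized.

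Nor do the documents support saying that the current rule almost never fires. Early in accrual it can, as the simulation shows. The loss of sensitivity is at middle to full accrual, which is also when most Stage 3 exposure accumulates.

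Finally, arm rates of 40% to 50% are high, and the nephritis data show no excess of serious infection with voclosporin (12% against 13%). The calculation shows what the rule can detect. It does not predict such an excess.

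**Conclusion.** The point holds for the two rate triggers. Followed as written, they omit flares and serious infections in participants who were withdrawn from lupus drugs and never randomized, and they need 36 affected participants at full accrual when about 42 receive the combination. For an assumed arm rate of 40% to 50% and 5% to 10% elsewhere, the chance of firing at n = 120 is between 0.007% and 5.7%, against 91% to 99.6% for the same 30% threshold within the arm. These figures rest on the plan's expected Stage 3 numbers and on assumed event rates. They do not mean that the DSMB would be unaware of such events; they mean that the automatic rate rule would usually not be what brings it together. This is a worthwhile, inexpensive improvement to safety oversight and not a fatal defect.

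**What to change.** In section 12.8.2.2 and the synopsis, keep the existing triggers and thresholds and add the same counts on two further denominators:

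- **Stage 3:** re-randomized participants, tabulated by Stage 3 arm by the SCCC for the DSMB only.
- **Stage 1:** everyone who received a corticosteroid injection or began drug withdrawal, whether or not later randomized. State that Stage 1 events in people later randomized count here.

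The data already arrive through AE, SAE and BILAG A reporting, and the SCCC performs the randomization, so the work is protocol wording and one tabulation.

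The cost is more ad hoc meetings. For infections, 3 of the first 10 occurs by chance with probability 7% at a true rate of 10% and 13% at a rate of 13%. Over both limbs in a 42-person arm, the false-alarm rate is about 8% and 16%. At 13%, treating the two Stage 3 arms as independent, at least one fires with probability 1 − 0.84² = 29%. Section 12.8.2.2.1 lets the study proceed pending review of a flare or infection trigger. If the DSMB has not met within 2 weeks, however, consenting, screening and Stage 2 randomization stop until it completes its review. The amendment should state this and plan for prompt meetings.
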